## **ABSTRACT**

### **Aims**

Robot-assisted total knee arthroplasty (raTKA) may improve implant positioning, soft-tissue balance, and early recovery, but high-quality randomised evidence is limited for raTKA in general, and imageless raTKA systems in particular. The MARVEL trial aims to compare robot-assisted TKA following a functional alignment strategy using the imageless VELYS Robot Assisted Solution with conventional manual jig-based TKA in patients undergoing primary TKA for osteoarthritis.

The study is specifically designed to address the principal UK National Institute for Health and Care Excellence (NICE) 2025 Early Value Assessment evidence domains for robot-assisted orthopaedic surgery, including patient-reported outcomes, safety, subgroup effectiveness, healthcare resource use, cost-effectiveness, and implementation-related outcomes.

### **Methods**

MARVEL is a pragmatic, multicentre, parallel-group, participant- and outcome assessor-blinded randomised controlled trial. Adults undergoing primary TKA for knee osteoarthritis will be randomised 1:1 to manual TKA or VELYS raTKA using the same implant platform. The primary outcome is change in Forgotten Joint Score from baseline to six months postoperatively.

Secondary outcomes include additional patient-reported outcome measures, radiographic alignment, intraoperative digital metrics, adverse events, subgroup analyses, health service resource use, surgical efficiency, clinician task load, and health economic outcomes. A nested motion analysis laboratory sub-study will assess objective biomechanical outcomes, and an internal pilot will assess feasibility, retention, intervention fidelity, safety, and completeness of primary outcome data. The target sample size is 346 participants in total, with 173 participants per group.

### **Discussion**

MARVEL is designed to provide randomised evidence on the clinical effectiveness, safety, biomechanical effects, implementation impact, and economic value of imageless robot-assisted functional alignment TKA compared with conventional manual TKA. By integrating patient-reported outcomes with radiographic, intraoperative, biomechanical, efficiency, and cost-effectiveness data, the study is intended to address major current evidence gaps and inform future adoption of raTKA in routine orthopaedic practice.

## **TAKE HOME MESSAGE**

MARVEL is a large, investigator-initiated, multicentre, blinded randomised controlled trial with multidomain investigations evaluating whether imageless robot-assisted functional alignment TKA using VELYS Robot Assisted Solution improves patient outcomes over standard manual jig-based TKA. It is designed to address the UK National Institute for Health and Care Excellence 2025 Early Value Assessment evidence domains for robot-assisted orthopaedic surgery: patient-reported outcomes, safety, subgroup effectiveness, healthcare resource use, cost-effectiveness, and implementation-related outcomes.

## **SPIRIT-COMPLIANT STRUCTURED SUMMARY**

### **Title**

Manual arthroplasty versus VELYS robot-assisted functional alignment in total knee arthroplasty (MARVEL): a pragmatic, multicentre, blinded randomised controlled trial with multidomain investigations.

### **Trial design**

Pragmatic, multicentre, parallel-group, superiority randomised controlled trial with 1:1 allocation. Nested components include an internal pilot, a motion analysis laboratory sub-study, and evaluations of surgical efficiency, task load, and clinician experience.

### **Setting**

Secondary care orthopaedic centres in the United Kingdom. The coordinating centre is Golden Jubilee University National Hospital, Clydebank, UK.

### **Participants**

Adults aged 18 years or older with primary knee osteoarthritis requiring primary total knee arthroplasty, suitable for either robot-assisted or manual TKA, able to provide written informed consent, and able and willing to complete follow-up assessments. Key exclusions include inflammatory arthritis, significant symptomatic hip/ankle/contralateral knee osteoarthritis, prior major surgery or injury to the index knee, neuromuscular gait disorders, BMI > 45 kg/m^2, major coronal or fixed flexion deformity, likely need for non-standard implants or constraint, inability to comply with follow-up, or contraindications to the surgical technique.

### **Interventions**

Participants will be randomised to manual TKA using conventional jig-based instrumentation or VELYS robot-assisted TKA using a functional alignment strategy. All patients will receive a cemented Attune prosthesis with a medial stabilised polyethylene insert. Perioperative care will otherwise be standardised across groups.

### **Primary outcome**

Change in Forgotten Joint Score from baseline to six months postoperatively.

### **Secondary outcomes**

Secondary outcomes include additional PROMs, radiographic alignment, intraoperative metrics, surgical efficiency, clinician task load, health service resource use, adverse events, and biomechanical outcomes in the motion analysis laboratory sub-study.

### **Sample size**

346 participants in total, with 173 per group, allowing for 15% loss to follow-up. The motion analysis laboratory sub-study will recruit 52 participants.

### **Randomisation and blinding**

Randomisation will be performed 1:1 using a secure web-based REDCap system with computer-generated permuted blocks, stratified by recruitment centre. Participants and outcome assessors will be blinded; surgeons cannot be blinded. Unblinding will occur only if required for urgent clinical management or participant safety.

### **Recruitment and follow-up**

Recruitment is planned from 01 April 2026 to 01 April 2029. Participants will be followed for 12 months, with the primary endpoint assessed at six months. Longer-term survivorship observation will continue for at least 10 years through follow-up and registry linkage.

### **Trial registration**

ClinicalTrials.gov, registration pending.

### **Sponsor and funding**

The sponsor is Golden Jubilee University National Hospital, Clydebank, UK. The study is investigator-initiated and funded by DePuy International Ltd, with the design, conduct, analysis, and reporting remaining under the control of the academic investigators.

### **Data availability**

The statistical analysis plan will be available on reasonable request. Following publication of the primary results, de-identified individual participant data, the data dictionary, and statistical code will be considered for sharing with bona fide researchers on reasonable request, subject to sponsor approval and governance requirements.

## INTRODUCTION

Osteoarthritis (OA) of the knee is one of the most prevalent causes of pain and disability globally. Total knee arthroplasty (TKA) is a highly effective treatment for end-stage disease, providing excellent long-term implant survivorship. However, despite advances in implant design and surgical techniques, between 10-20% of patients remain dissatisfied following surgery, citing persistent pain, stiffness, or limitations in function. An evolving body of research suggests that clinical and functional outcomes may be improved by the adoption of modern alignment and balancing strategies facilitated by robot-assisted systems (RAS) in arthroplasty.

Conventionally, TKA is performed using manual instrumentation to determine limb alignment, bone resection, component sizing, and joint balance evaluation, with cutting blocks and a handheld oscillating saw to execute a preoperative plan. While this approach remains the standard of care and has produced excellent long-term outcomes, it is inherently limited by its reliance on indirect anatomical references and manual execution. Deviations in guide positioning, sawblade control, or instrument calibration can result in alignment errors and variable bone resections, and intraoperative assessment of ligament balance and joint gaps is subjective. This may produce variability in component positioning, limb alignment, and soft-tissue balance, which can influence functional outcomes and implant longevity.

Manual (m) TKA is most commonly executed in accordance with a mechanical alignment (MA) philosophy, which aims to achieve a neutral hip-knee-ankle (HKA) axis and horizontal knee joint line obliquity (JLO) by making bone resections perpendicular to the mechanical axes of the femur and tibia and using soft tissue releases to achieve a balanced joint. This standardised approach evolved because implant design and fixation methods were believed to have greater longevity when positioned perpendicular to the mechanical load-bearing axis, thereby minimising asymmetric stresses across the prosthesis during ambulation. Additionally, the inherent variability associated with conventional manual instrumentation made it prudent to aim for a neutral alignment 'middle ground,' reducing the risk of extreme malposition that could compromise implant fixation, wear characteristics, or overall limb mechanics. However, MA does not account for the considerable individual variation in constitutional limb alignment and JLO seen in the population, with only 15% of healthy knees exhibiting neutral HKA and JLO. This may be associated with suboptimal outcomes in some patients, and explains why the number of patients that are dissatisfied after TKA remains at 10% to 20%.

Kinematic alignment (KA) has gained popularity as an alternative to MA and aims to replicate the pre-arthritis anatomy and kinematic axes, with some evidence suggesting this leads to better knee function, and variations are described based on the surgical process by which it is achieved. However, KA suffers the same limitations as MA when using conventional instrumentation, and these may even be of greater consequence when employing a KA strategy because of the limited accuracy and reproducibility of manual tools when evaluating knee balance and executing bony resections. Furthermore, inaccuracies made when following KA rather than MA strategy may occur further from the mechanical axis of the limb, and therefore be of greater consequence. In practice, most modern mTKA strategies borrow principles from multiple philosophies along the MA-KA spectrum to produce a safely positioned, balanced prosthetic joint.

The introduction of robot-assisted surgery in arthroplasty has provided surgeons with tools for multi-dimensional reconstructive modelling and precise bone resection that preserves the soft tissue envelope, and these systems can be used with any TKA philosophy. Suggested benefits of RAS include fewer errors of resection, balance, iatrogenic injury, and implant position, which may improve short and long-term outcomes. Systems that permit precise, dynamic intraoperative evaluation of knee function have allowed surgeons to move away from conventional MA towards more ‘personalised’ arthroplasty strategies. This has facilitated the evolution of functional alignment (FA), which builds on the KA principles of restoration of native knee kinematics while prioritising accurate restoration of soft tissue balance.

There is good evidence suggesting that robot-assisted TKA (raTKA) is associated with improved early postoperative recovery and a reduction of errors in component positioning. The literature is limited by heterogeneous techniques, a lack of standardisation, and a shortage of large, high-quality randomised controlled trials (RCTs). Additionally, previous studies have seldom included objective assessments of biomechanics or explored the relationship between intraoperative alignment and post-operative outcomes. Furthermore, much of the literature evaluating RAS in knee arthroplasty is focused on computerised tomography (CT) guided systems such as Mako Robot-arm Assisted Surgery (Styker Inc., Kalamazoo, MI, USA). Imageless systems like the VELYS Robot-assisted Solution (VRAS; Johnson & Johnson MedTech, Warsaw, IN, USA) capture all data intraoperatively, with a focus on real-time assessment of landmarks, stability, and soft tissue envelope tracking through a range of motion. It is possible that such systems could guide safe, consistent joint replacement surgery that prioritises the restoration of native knee kinematic function, and negates the economic, time, resource, and radiation costs associated with CT-guided

systems. However as imageless systems become widespread, more research is required to address key evidence gaps.

The current literature on the use of VRAS in TKA demonstrates early promise, though the evidence base remains limited. Most available studies are small retrospective cohort analyses, with no RCTs published to date. Existing data suggest that VRAS improves the precision of component positioning compared with both manual and navigated TKA. Additional reported benefits include improved early functional outcomes, a relatively short learning curve, a safety profile at least equivalent to manual TKA, and reduced rates of soft tissue release and inadvertent injury. Despite these encouraging findings, higher-quality research, particularly adequately powered RCTs assessing appropriate patient-reported outcome measures (PROMs) and enabling subgroup analyses, remains essential.

Many patients believe RAS guarantees better outcomes or faster recovery; however, current evidence is insufficient to support such claims. Alongside these misconceptions, concerns are expressed regarding the radiation exposure associated with pre-operative CT scans required for certain RAS systems. Notably, despite these concerns, a majority of patients indicate a preference for raTKA over mTKA when given the choice. This highlights a substantial cohort who would favour an imageless system, emphasising the importance of providing accurate, transparent information about such technologies.

Guidance on the information that should be generated and communicated has been outlined by the UK National Institute for Health and Clinical Excellence in its ‘early value assessment’ of RAS for orthopaedic procedures. This assessment identifies key evidence priorities for the six major orthopaedic RAS technologies over the next three years, including: the impact on patient quality of life and healthcare resource use; technology-specific utilities data and additional resource use data to inform economic modelling; and the clinical effectiveness of RAS in defined patient subgroups. These priorities align closely with the current knowledge gaps relating to the VELYS system in particular. The MARVEL Project (manual arthroplasty versus VELYS robot-assisted functional alignment in total knee arthroplasty) aims to address these gaps with a comprehensive evaluation of VRAS.

This multicentre, pragmatic, parallel-group, blinded RCT will compare VELYS robot-assisted functional alignment with conventional mTKA. The trial will employ a clearly defined, reproducible surgical protocol that will incorporate evaluation of the study cohort using: established clinical and patient-reported outcome measures (PROMs); gold-standard three-dimensional (3D) motion analysis

to objectively evaluate functional outcomes; detailed examination of intraoperative knee kinematics, pre-/post-operative hip-knee-ankle radiographic data, and healthcare system effects including economic, efficiency, and human factor measures.

### ***Objectives***

The primary objective is to compare knee-specific health outcomes in patients undergoing TKA performed with VELYS robot-assisted (raTKA) using functional alignment versus TKA performed manually (mTKA) using conventional instrumentation. The primary outcome measure will be differences between the two intervention groups (using an intention-to-treat approach) with regard to change in Forgotten Joint Score (FJS) preoperatively versus 6 months post-surgery. The secondary objectives are to:

- 1) Compare PROMs (FJS, EQ-5D-5L, Oxford Knee Score [OKS], satisfaction [numeric rating scale; NRS], 4-part Likert scale], pain [101-point scale VAS]) at 6 weeks, 6 months, and 12 months;
- 2) Correlate these outcomes with radiographic alignment and intra-operative data;
- 3) Evaluate biomechanical outcomes using motion analysis laboratory assessment;
- 4) Functional and activity-related outcomes;
- 5) Evaluate the economic and efficiency effects of imageless raTKA relative to mTKA;
- 6) Evaluate the human factor effects of introducing a new RAS into healthcare teams;
- 7) Assess surgical safety and the incidence of adverse events in both groups.

### ***Null hypothesis***

The null hypothesis is that functionally aligned raTKA using the VELYS imageless system does not result in a greater early improvement in knee-specific outcomes, as measured by change in Forgotten Joint Score at 6 months, compared with conventional mTKA.

## **METHODS**

### ***Study design***

The study is designed as a multicentre, pragmatic, parallel-group blinded RCT. There are nested modular study components, including: an internal pilot to determine safety and practicability; a motion analysis evaluation, and a task load, efficiency, and clinician perspective evaluation. The lead centre for the study will be the Golden Jubilee University National Hospital (GJUNH). Additional centres will be based in the United Kingdom and Irish regions. All participating surgeons are high-volume arthroplasty surgeons (performing approximately 100 knee arthroplasties annually) and have extensive experience with robot-assisted surgery.

### ***Surgeons and training***

All participating surgeons are high-volume arthroplasty surgeons (performing approximately 100 knee arthroplasties annually) and have extensive experience with robot-assisted surgery. Studies evaluating the learning curve of the VELYS system found that proficiency was reached after between 5-9 cases, and there was no significant difference in outcomes for patients that underwent raTKA early versus late on the operator's experience curve.

To minimise any learning curve effects and variability between centres, all surgeons will have completed manufacturer-delivered training and credentialling using both the manual and robotic systems, and a minimum of 20 Attune TKA non-trial cases will have been completed by all surgeons (comprising 10 manual Attune and 10 VELYS-assisted cases) before they recruit trial participants. A subgroup analysis of TKA performed early versus late on the clinical experience will be performed as part of the interim pilot study to evaluate for differences in outcomes and adverse events, and a sensitivity analysis will be performed if indicated.

### ***Sample size***

The sample size calculation is based on detecting a minimum clinically important difference (MCID) of 7 points in the FJS at six months post-operatively. This is informed by Alton et al (2025), and a standard deviation of 24 points, as reported in Clement et al., 2021. Using a one-sided alpha of 0.05 and a power of 80%, it was calculated that 147 participants per group would be required. To account for an anticipated 15% loss to follow-up, the final recruitment target is 173 participants per group, yielding a total study population of 346 participants.

Outcome data from the internal pilot (the first 100 study participants who have completed their 6-month follow-up) will be analysed. A blinded pooled estimate of the outcome variance will be computed and used in a pre-specified sample size re-estimation algorithm. The analysis team will remain blinded to treatment allocation; any sample size adjustments will be made according to the pre-specified rules to preserve type I error.

For the motion analysis sub-study, a sample size of 52 participants (26 in the raTKA and mTKA groups respectively) has been determined to provide sufficient power to detect expected differences in peak medial knee contact force compared with matched healthy controls.

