### ***Statistical analysis***

All analyses will adhere to CONSORT reporting standards. A detailed statistical analysis plan will be finalised with the Trial Steering Committee before any formal analyses are undertaken. Baseline characteristics will be summarised to assess comparability between treatment groups. Simple descriptive statistics will follow standard conventions, including means and standard deviations or medians and interquartile ranges as appropriate for continuous variables, and counts and percentages for categorical data.

The primary analysis will examine differences between the two intervention groups (using an intention-to-treat approach) with regard to their change in FJS (preoperatively versus 6 months post-surgery). A Student's independent t-test will be used to compare mean scores between groups. Assumptions of normality and equality of variances will be assessed using diagnostic plots and Levene's test. If variances are unequal, the Welch's t-test will be applied. The results will be reported as mean differences with 95% confidence intervals and p-values.

Secondary outcomes will be analysed similarly, appropriate to the type and distribution of the data. Categorical outcomes, such as patient satisfaction and complication rates, will be compared between groups using the chi-square test. If any expected cell count is less than five, Fisher's exact test will be applied. Effect sizes will be reported alongside these comparisons using risk ratios or odds ratios with 95% confidence intervals to provide a measure of the magnitude and precision of differences between groups.

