### ***Multiple testing***

Formal adjustment for multiple comparisons will be applied only to analyses of the primary outcome. Secondary outcome analyses will be considered exploratory and will not undergo multiplicity correction, as such adjustments may be overly conservative and risk masking clinically meaningful effects. Results for secondary outcomes will therefore be presented with unadjusted p-values, effect sizes, and 95% confidence intervals to support interpretation rather than definitive inference.

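### The sample size uses a one-sided 5% test, but the primary result is to be reported with a 95% confidence interval, and the protocol does not say which of the two decides superiority

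*Protocol*

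**What the plan says.** Four parts of the protocol bear on the primary decision.

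- **Null hypothesis.** It is directional: raTKA does not give a larger improvement in FJS at 6 months than mTKA. The structured summary accordingly describes the design as "Pragmatic, multicentre, parallel-group, superiority randomised controlled trial with 1:1 allocation".
- **Sample size.** The target is "detecting a minimum clinically important difference (MCID) of 7 points in the FJS at six months post-operatively", with "a standard deviation of 24 points". The test level is one-sided: "Using a one-sided alpha of 0.05 and a power of 80%, it was calculated that 147 participants per group would be required". Allowing for 15% loss gives 173 per group and 346 in total. A blinded re-estimation of the variance follows the internal pilot.
- **Statistical analysis.** The primary comparison is an independent-samples t-test, or Welch's test if variances differ. On presentation, the section says: "The results will be reported as mean differences with 95% confidence intervals and p-values". It gives no alpha, no sidedness for the p-value or interval, and no rule for declaring superiority.
- **Multiple testing.** "Formal adjustment for multiple comparisons will be applied only to analyses of the primary outcome". The protocol has one primary outcome, at one time point, between two groups.

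Nowhere does the protocol mention a 90% interval or a one-sided bound, or give a reason for choosing one-sided 5%. The Sample size entry in the structured summary gives the numbers but not the one-sided alpha.

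**The concern.** A conventional 95% interval excludes zero in favour of raTKA exactly when a one-sided test rejects at 2.5%. The trial is sized for rejection at one-sided 5%, which is an easier threshold. Both sections can be followed to the letter and still give different answers on the same data: a one-sided p-value below 0.05 beside a 95% interval that includes zero.

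Two things are at stake. The first is what counts as a positive trial on its primary outcome, which should not be left open until the data are in. The second is the power claim. The 80% belongs to the one-sided 5% test and does not carry over to a conclusion drawn from the 95% interval, which many readers will treat as the test.

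**Working it through.** **Inputs, all from the Sample size section:** difference 7, SD 24, 147 evaluable per group, alpha 0.05 one-sided, power 80%, loss 15%. Assumption: the 95% interval in the Statistical analysis section is the ordinary two-sided one.

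**1. Reproduce the plan's figure.**
- The smallest n per group with noncentral-t power of at least 80% at one-sided 5% is 147. At n = 146 the power is 79.99%, and at n = 147 it is 80.2%. The normal approximation gives 146.
- 147 / 0.85 = 172.9, so 173 per group and 346 in total.
- The two-sided calculation gives 185 (normal) or 186 (t), so it does not yield 147. The one-sided alpha was really used and is not a slip of wording.

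**2. Standard error of the difference.**
- SE = 24 × √(2/147) = 2.80 points, with 292 degrees of freedom.
- Noncentrality for 7 points: 7 / 2.80 = 2.50.

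**3. Thresholds for the observed difference.**
- One-sided 5%: 1.650 × 2.80 = 4.62 points.
- 95% interval excluding zero: 1.968 × 2.80 = 5.51 points.
- Between about 4.6 and 5.5 points the two rules disagree.

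**4. Power under each rule (noncentral t, true difference 7 points).**

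| Rule | 147 per group | 173 per group (no loss) |
|---|---|---|
| One-sided 5% | 80.2% | 85.6% |
| Two-sided 5% (95% interval) | 70.3% | 77.2% |

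If the true difference is 7 points, the chance of landing in the zone of disagreement is 80.2% − 70.3% = 9.9%.

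**5. What 147 per group can detect at 80% under the 95% interval rule.**
- Normal approximation: (1.960 + 0.842) × 2.80 = 7.84 points. Noncentral t: 7.87, so about 7.9 points.
- For scale, 80% power for 7 points under that rule would need 186 evaluable per group; 186 / 0.85 = 218.8, so 219 recruited per group and 438 in total.

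**6. Multiple testing.** The calculation in step 1 spends the full 5% on one comparison. Nothing in it allows for an adjustment.

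**The case against.** The strongest reply is that the protocol is coherent on its own terms. The null hypothesis is directional, the sample size is one-sided, and 147 is right for that test. The Statistical analysis section says only how results will be reported. A 95% interval can stand beside a one-sided test as an estimate, and the SAP may set the sidedness of the p-value.

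Much of this stands, and it rules out several stronger readings that a reader might infer:

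- **That the sample size arithmetic is wrong.** It is not. Both 147 and 173 reproduce from the stated inputs.
- **That the trial simply has 70% power.** This holds only if the 95% interval is the decision rule, and the protocol never says so. Under a one-sided 5% decision the 80% is correct.
- **That the plan allows twice the proper false-superiority rate.** The 5% one-sided level is openly declared. The 2.5% comparison comes from the usual reading of a 95% interval, not from a benchmark stated in the protocol.
- **That the Multiple testing section costs a calculable amount of power.** The other FJS time points and the absolute FJS are listed as secondary and are exempt from adjustment. There is no family of primary tests to split alpha over, so any Bonferroni figure would be invented.

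The reply does not remove the inconsistency. A directional hypothesis does not set alpha: one-sided 2.5% is equally directional and would agree with the 95% interval. Nor is this merely detail left to the SAP, because the protocol fixes both the design alpha and the interval, and they do not match. The blinded re-estimation revises only the variance and would carry the mismatch forward.

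**Conclusion.** This is an internal inconsistency in how the primary result is to be judged, and it should be corrected before outcome data accrue. The design alpha is one-sided 5%, the reported interval corresponds to one-sided 2.5%, and no rule says which governs.

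Its size depends on the reading. Under the one-sided test, power is 80.2% for 7 points. Under the 95% interval it is about 70%, with 80% reached at about 7.9 points. Observed differences from about 4.6 to 5.5 points would be read in opposite ways.

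These figures assume SD 24, 147 evaluable per group, equal variances and an ordinary two-sided interval. A different SD would move the thresholds, but the two rules would still differ.

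**What to change.** State one decision rule in Null hypothesis, Sample size and Statistical analysis, and use the same alpha in the blinded re-estimation. Either route is coherent:

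- **(a) Two-sided rule.** Declare superiority when the two-sided 95% interval for the difference excludes zero in favour of raTKA. Restate the power of 147 per group as about 70% for 7 points, or 80% for about 7.9 points. The cost is a less favourable stated power. No participants need be added if that power is accepted; restoring 80% for 7 points would take the 438 worked out above.
- **(b) One-sided rule.** Keep the one-sided 5% test, say so in Statistical analysis and in the structured summary, and report the matching 90% interval or one-sided 95% bound. The 80% then stands. The cost is a less conventional interval.

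Under either route, replace the adjustment sentence in Multiple testing with a statement that the single primary comparison is tested at the full alpha without adjustment, since the sample size allows for none.
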